Specific Aim 3. Characterize functional dynamics of immune cell subsets in MDS patients pre- and post- anti-PD1 therapy: Using multi-color flow cytometry, we will examine CD4+, CD8⁺ T-cell subpopulations (expressing CD45RA, CCR7, and CD27), Foxp3⁺ regulatory T cells (T-reg), and also natural killer (NK), NKT cells and dendritic cells (DC) with the following panel of mAbs: CD16 and CD56 (markers of NK cells and NKT cells), CD11c (a marker of myeloid DCs) and CD123 (a marker of plasmacytoid DCs) in BM aspirate and PBMCs of MDS patients obtained as above (pre- and post- anti-PD1). We will also analyze PD-1 expression and intracellular molecules such as Foxp3, Ki67, Eomes and Granzyme B (GzmB). All flow cytometric acquisition will be carried out using an LSR II (BD) or FACS Calibur (BD) and acquired data will be analyzed using FlowJo software (TreeStar). The changes in these subsets will be correlated with clinical responses.

Potential pitfall and alternative methods (for SA2 & SA3): We will possibly have limited number of cells in BM aspirate, so we will prioritize patient samples if not enough to perform all the assays described in SA2, SA3. Our priority will be to carry out SA3 since SA2 will be assessed by IHC. Alternatively, we will analyze the immune profile combining a high-throughput technique that will allow us to study more than 20 markers in a single cell analysis using mass cytometry (CyTOF). These techniques will provide information about the architecture of the tumor microenvironment (TME) (i.e. BM) and the distribution of markers of interest detected with CyTOF. CyTOF-based single cell analysis is a new technology that combines flow cytometry with metal-conjugated antibodies detected by mass spectrometry permitting higher order multiplexing (up to 100 molecules) on a single cell analysis⁹¹. For this assay, the staining will be performed

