using MaxPar Human T Cell Phenotyping Panel Kit (CD11a, CD4, CD8a, CD16, CD25, CD45, CCR7, CD69, CD45RO, CD44, CD27, CD45RA, CD3, CD57, HLA-DR, and CD127) along with CD28, CD117, and CD95), modified MaxPar human AML phenotyping panel (added CD10, CD13, CD16 on top of CD19, CD117, CD11b, CD64, CD7, CD123, CD45, CD33, CD15, CD34, CD3, CD44, CD38, HLA-DR, CXCR4) for surface staining as per manufacturer's protocol. Additionally, after fixation and permeabilization, cells will be stained with anti-human Ki-67-151Eu (B56; BD Pharmingen Ab conjugated with lanthanide MaxPar Europium Chloride 151Eu using the MaxPar X8 Ab labeling kit) for 30 min at room temperature. Cells will be acquired on CyTOF 2 instrument (DVS; Fluidigm Sciences). All data will be analyzed and graphs generated using the DVS Cytobank software (Cytobank).

STATISTICAL CONSIDERATIONS and ANALYTICAL PLAN

SPECIFIC AIM 1:

The quantitative change in MDSCs (% MDSCs by flow cytometry, QIF score by AQUA) during treatment with the ENT/anti-PD1 combined therapy will be estimated using mixed effects models to take into account the within-patient correlation of measurements over time. Likelihood ratio tests will be performed to confirm if random intercepts and slopes are necessary in the model. The fixed effect for change in MDSCs over time will be evaluated for significance. The variability in the rate of change in MDSCs across patients will also be examined. The association between the clinical outcome and a meaningful reduction in MDSCs, which will be defined after a review of the data, will be assessed with the chi-square test. The quantity of MDSCs at baseline and during treatment as continuous variables can also be compared between responding and non-responding patients using a t-test or Mann-Whitney U-Test, if more appropriate. We will apply the same statistical analyses for the expression of arginase I and ROS and arginase activity of MDSCs (SA 1.3) and suppressive activity of MDSCs by measuring T-cell proliferation & IFN- γ production (SA 1.4).

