SPECIFIC AIM 2: MDACC study demonstrated 20% of leukemic blasts express PD-L1 when positive is considered when more than 5% CD34+ blasts express PD-L1 by IHC while in normal CD34+ controls, PD-L1 is nearly 0%¹³. An association of clinical response with the expression of PD-L1 MDS CD34+ blasts will be assessed by a Pearson chi-square test on a 2x2 table of frequencies. The dependent variable will be defined as response (yes versus no), and flow cytometry/IHC categories (negative vs positive) will be the independent variables. We will also monitor the dynamic change of PD-L1 expression over the course of treatment and its correlation with clinical response. Longitudinal measurements of PD-L1 will be examined using mixed-effects modeling.

SPECIFIC AIM 3: Statistical analyses of the frequency of CD8+, CD4+, Foxp3 Tregs, CD8+/Foxp3+ Tregs, T_{CM}/T_{EMRA}, T_{EM}/T_{EMRA}, the percentage of Ki67 and Gzmb in PD-1+, Eomes+ CD8 T cells to compare changes over time from baseline to several time-points will be performed by using mixed effects modelling with a Benjamini-Hochberg correction to control for false discovery rates.

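### The CyTOF alternative for cell-poor marrows omits PD-1, Foxp3, Eomes and Granzyme B, so half of the Aim 3 quantities cannot be computed from marrow samples measured that way

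*Combined protocol and SAP*

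**What the plan says.** Three parts of Appendix J bear on this point.

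- **Planned assay (Specific Aim 3).** Multi-colour flow cytometry on marrow aspirate and on peripheral blood mononuclear cells (PBMCs). The markers include "We will also analyze PD-1 expression and intracellular molecules such as Foxp3, Ki67, Eomes and Granzyme B".
- **Alternative method (the potential-pitfall paragraph for SA2 and SA3).** It warns: "We will possibly have limited number of cells in BM aspirate, so we will prioritize patient samples if not enough". It first gives Aim 3 priority over Aim 2. It then continues: "Alternatively, we will analyze the immune profile combining a high-throughput technique", and names CyTOF. The reagents are a T-cell phenotyping kit with three added markers, a modified AML phenotyping panel and, after permeabilization, one antibody: "Additionally, after fixation and permeabilization, cells will be stained with anti-human Ki-67".
- **Analysis (Statistical Considerations, Specific Aim 3).** Mixed-effects models of "Statistical analyses of the frequency of CD8+, CD4+, Foxp3 Tregs, CD8+/Foxp3+ Tregs", the two memory-to-TEMRA ratios, and "the percentage of Ki67 and Gzmb in PD-1+, Eomes+ CD8 T cells to compare changes over time from baseline to several time-points", with a Benjamini-Hochberg correction.

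PD-1 expression in bone marrow is also named in the protocol body, in the exploratory objective (Section 1.3) and the synopsis list of exploratory endpoints.

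**The concern.** The alternative assay was not matched to the analysis it is meant to feed. The flow panel covers every marker that the Aim 3 quantities need, and the CyTOF panel does not. The analysis section gives no substitute definition and no rule for samples run on CyTOF.

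The route is offered because cells may be scarce, so the resulting gaps would not be random: they would fall on the poorer marrows. In a trial of at most 27 patients there is little to spare. Cells already stained and run without these antibodies cannot supply the missing readings later.

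There is a second, conditional issue. If some marrow samples are measured by flow and others by CyTOF, a difference between platforms can enter the estimated change over time in the quantities that both can measure.

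**Working it through.** **1. Size of the CyTOF panel.** Inputs: the reagent list in the Appendix J pitfall paragraph.

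- T-cell kit: 16
- Added to it (CD28, CD117, CD95): 3
- Modified AML panel: 18 (3 added + 15)
- Intracellular (Ki-67): 1

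Total entries = 16 + 3 + 18 + 1 = 38. Six markers appear twice (CD3, CD16, CD44, CD45, CD117, HLA-DR), so distinct markers = 38 − 6 = 32. This agrees with the only count the plan gives for the assay, more than 20.

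**2. Each Aim 3 quantity against the 32 markers.**

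| Quantity in the analysis section | Markers needed | Not in the CyTOF list |
|---|---|---|
| CD8+ frequency | CD3, CD8 | none |
| CD4+ frequency | CD3, CD4 | none |
| Foxp3 Tregs | CD4, Foxp3 | Foxp3 |
| CD8+/Foxp3+ Tregs | CD8, Foxp3 | Foxp3 |
| TCM/TEMRA | CD45RA, CCR7 | none |
| TEM/TEMRA | CD45RA, CCR7 | none |
| % Ki67 in PD-1+ Eomes+ CD8 cells | CD8, PD-1, Eomes, Ki-67 | PD-1, Eomes |
| % GzmB in PD-1+ Eomes+ CD8 cells | CD8, PD-1, Eomes, GzmB | PD-1, Eomes, GzmB |

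Not computable: 4/8 = 50%.

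**3. Sensitivity to how the list is counted.** Taking Ki67 and GzmB as one quantity gives 3/7 = 43%. Taking PD-1+ and Eomes+ as separate populations gives 2 × 2 = 4 reinvigoration quantities, hence (2 + 4)/(6 + 4) = 6/10 = 60%. The share lies between 43% and 60% on any of these readings.

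**4. Share of marrow data lost.** If a fraction *f* of marrow samples is measured by CyTOF instead of flow, the same fraction *f* of the marrow observations on those four quantities is missing. The documents give no rate of low-yield marrows, so *f* is unknown and could be close to zero.

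**5. Mixed platforms, if they occur.** Suppose CyTOF reads a quantity δ higher than flow, and a fraction *f*ₜ of marrow samples at visit *t* is on CyTOF (*f*₀ at baseline). With no platform term, the apparent mean change from baseline is the true change + δ(*f*ₜ − *f*₀). The bias is zero only if the platforms agree or the mix is the same at both visits. The documents give neither δ nor *f*ₜ.

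**6. After adding the four markers.** 32 + 4 = 36 distinct markers, and all 8 quantities become computable. If the T-cell and AML panels are run as two separate stains, with Ki-67 in the T-cell stain, that stain goes from 16 + 3 + 1 = 20 to 24.

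**The case against.** The strongest reply has four parts.

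- **Blood is unaffected.** Flow is also run on PBMCs, and Section 9.1 collects blood alongside marrow. This stands. A reader might infer that these endpoints are lost altogether for patients with poor marrows. The documents do not support that: only the marrow values are at risk. They still matter, since the specific aim is stated for MDS marrow.
- **CyTOF may not replace flow.** The first response to few cells is to give Aim 3 priority, so some cell-poor marrows may still get the full flow panel, and the CyTOF text can be read as extra profiling. This stands in part. The plan states no visit-by-visit switch, so one should not be read into it. But a paragraph on alternative methods that follows a low-yield warning most naturally describes replacement, and the plan should say which it means.
- **Other routes exist.** Clot sections may give PD-1 and FOXP3 levels if tissue suffices (SA 1.2), and CD25 with CD127, both in the CyTOF kit, could approximate Tregs. Neither gives the quantities as defined. Clot sections have no Eomes or Granzyme B stain, and the plan defines Tregs by Foxp3 and names no surrogate.
- **It is exploratory.** This stands and limits the weight of the point.

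It is also tempting to say that the predictive markers are the ones lost. Appendix J's paragraph on exploratory biomarkers names two: CD8+ frequency and the CD8+/Treg measure. The first survives on CyTOF. The Ki67/GzmB reinvigoration finding is reported there as a murine observation and is not itself called predictive.

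**Conclusion.** The omission is confirmed by a direct marker check. For any marrow sample measured by CyTOF instead of flow, 4 of the 8 Aim 3 quantities (43% to 60% under other counts) cannot be computed as the analysis section defines them. Nor can the flow measure of marrow PD-1 expression named in Section 1.3 and the synopsis.

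This rests on two readings: that the reagent list is the complete CyTOF panel, and that CyTOF can stand in for marrow flow. It does not extend to blood. No percentage of trial data lost can be given, because the documents offer no expected share of low-yield marrows. Platform bias over time is a possibility if both assays are used for marrow, not something the plan prescribes. Dose finding and the response-rate test are unaffected. The point is worth correcting because the change is small and has to be made before the samples are run.

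**What to change.** 1. In the Appendix J CyTOF panel, add PD-1 to the surface stain, and add Foxp3, Eomes and Granzyme B to the post-permeabilization stain alongside Ki-67. CD56 and CD11c are optional. They serve the NK/NKT and myeloid dendritic cell subsets in the Aim 3 flow panel but none of the eight analysed quantities. Including them brings the total to 36 + 2 = 38 markers.
2. State whether CyTOF replaces or supplements marrow flow.
3. Record the platform for each sample. If both are used for marrow, include platform as a fixed effect in the Aim 3 mixed model, or report a flow-only sensitivity analysis.

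The cost is a few conjugated antibodies and their validation, with no extra sample from the patient. Appendix J cites up to 100 molecules for CyTOF; that describes the technology in general, so the laboratory should confirm that the enlarged panel fits its instrument. A platform term is only a partial remedy: if cell yield decides the assay, platform and marrow cellularity remain partly confounded. A rule of one platform per patient is not practical, because yield is not known in advance. The added antibodies are therefore the essential change.

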13.2 Sample Size/Accrual Rate

We expect to accrue 1-2 patients with MDS per month once the study is open.

Currently there is no therapy that has been shown to prolong survival in MDS in the post-DNMTi setting and that the expected best response in patients receiving supportive care only in post-DNMTi setting is negligible (1% or less). It is generally accepted that a $\geq 15\%$ ORR in the post-DNMTi is clinically meaningful and would be worth further evaluation in larger studies.

The total number of patients enrolled in the study will range from 21 to 27. The null hypothesis response rate of 1% (only supportive care) will be rejected if we observe 2 or more favorable responses. These criterion has significance level between .02 and .03 using a one-sided binomial test. This criterion has power between .84 and .93 for testing an alternative response rate of 15% with the combination therapy. Therefore, we will treat a total of 21 patients in the combination arm (6 in the first part of the study and 15 in the second part of the study).

DOMESTIC PLANNED ENROLLMENT REPORT						
Racial Categories	Ethnic Categories				Total	
	Not Hispanic or Latino		Hispanic or Latino			
	Female	Male	Female	Male		
American Indian/ Alaska Native	1	1	1	1	4	
Asian	1	1	0	0	2	
Native Hawaiian or Other Pacific Islander	1	0	0	0	1	
Black or African American	1	1	1	1	4	
White	4	4	1	1	10	
More Than One Race	0	0	0	0		
Total	8	7	3	3	21	

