Potential pitfall (SA1): The quantity of MDSCs in BM samples is hard to predict. In addition to QIF, we will also perform flow cytometric analyses using the same markers (CD11b, CD33, HLA-

DR) as well as CD14, and CD15 to define granulocytic MDSCs (CD11b+/CD33+/HLA-DR-/CD15+) and monocytic MDSCs (CD11b+/CD33+/HLA-DR-/CD14+) in fresh aspirate simultaneously obtained with BM core biopsy.

We will prioritize patient BM aspirates if there is not enough to perform all of the assays described in SA1. Our first priority will be to measure the quantitative alteration of MDSCs pre- and post-anti-PD1 therapy/ENT by flow cytometry. We will measure the expression of arginase I, the generation of ROS (SA 1.3). We will then assess the arginase activity (SA 1.3) and the suppression assay (SA 1.4), and lastly measure arginase activity. Cryopreservation, decalcification and the type of collection tubes (heparin vs EDTA vs calcium phosphate) may affect the quantity or quality of MDSCs^{81,90}. We will stain fresh cells for flow cytometry and functional assay and clot section of BM for QIF assay⁸¹. We will also use EDTA tubes as described before if we see any significant difference of the quantity or quality of MDSCs depending on the types of tube⁹⁰.

Specific Aim 2. Evaluate whether PD-L1 expression in CD34+ blasts from MDS BM correlates with the response to anti-PD1 therapy: Clot sections of BM will be fixed. PD-L1 expression will be evaluated on MDS CD34+ blasts by IHC and QIF. Specimens will be classified as negative or positive if <5%, ≥5% of CD34+ cells are PD-L1 positive, respectively as previously described^{8,10,13}. Flow cytometry will be carried out on the BM aspirate to analyze the percentage of PD-L1 expressing CD34+ blasts in BM of MDS patients using rabbit anti-PD-L1 monoclonal antibody (E1L3N, Cell Signaling). Specimens will be classified as FACS negative or positive if <5%, ≥5% of CD34+ are PD-L1 positive, respectively. These studies will be performed at the beginning of trial and after the first cycle of ENT monotherapy, after every 2 cycles of combined therapy, and at progression or discontinuation from study

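### Aim 2 tests PD-L1 level against response only after a 5% cut; a comparison on the measured scale, as Aim 1 has, should be added and its time point named

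*Combined protocol and SAP*

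**What the plan says.** The Specific Aim 2 methodology in Appendix J measures PD-L1 on CD34+ blasts by IHC and QIF on clot sections, and by flow cytometry as a percentage on the aspirate. Each specimen is then reduced to two classes. For flow cytometry: "Specimens will be classified as FACS negative or positive if <5%, ≥5% of CD34+ are PD-L1 positive, respectively". The same 5% cut applies to IHC/QIF, with a reference to earlier studies.

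The Appendix J analytical plan for Specific Aim 2 then tests association with response by a Pearson chi-square on a 2x2 table: "The dependent variable will be defined as response (yes versus no), and flow cytometry/IHC categories (negative vs positive) will be the independent variables". It also intends to relate the change in PD-L1 over treatment to response and to fit mixed-effects models to the repeated PD-L1 values, but it names neither the scale nor the test for that correlation.

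For Specific Aim 1 the same analytical plan goes further: "The quantity of MDSCs at baseline and during treatment as continuous variables can also be compared between responding and non-responding patients", by t-test or Mann-Whitney. It extends this to arginase I, ROS, arginase activity and suppressive activity. PD-L1 is not included, and section 13.4 does not add it.

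**The concern.** Two quantitatively measured markers are handled differently, and no reason is given. For PD-L1, a patient at 6% and one at 60% count as the same, while patients at 4% and 6% count as opposites. In a large study this would cost some efficiency. Here the number of responders is so small that the classification of a single patient can turn a nominally significant table into an unremarkable one. The boundary itself is not stated consistently: the methodology counts 5% or more as positive, whereas the analytical plan describes the cited study's result in terms of more than 5%.

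At stake is how far the answer to Aim 2, whether PD-L1 expression goes with response, depends on one or two borderline readings.

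**Working it through.** **Expected responders.** Section 13.2 gives the sample size: "Therefore, we will treat a total of 21 patients in the combination arm", with "The total number of patients enrolled in the study will range from 21 to 27". The response rule is "The null hypothesis response rate of 1% (only supportive care) will be rejected if we observe 2 or more favorable responses", and "This criterion has power between .84 and .93 for testing an alternative response rate of 15% with the combination therapy". Under that rule the probability of rejection is 1 − (1−p)^n − n·p·(1−p)^(n−1).

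| n | p = .01 | p = .15 |
|---|---|---|
| 21 | .0185 | .845 |
| 27 | .0297 | .928 |

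These match the stated ranges of .02 to .03 and .84 to .93. At a 15% response rate the expected number of responders is 21 × .15 = 3.15, or 27 × .15 = 4.05. No alpha, power or sample size is stated for Aim 2, so I assume two-sided 5%.

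**Sensitivity to one patient.** Take 21 patients, 3 responders and 4 PD-L1 positives (19%).

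- With 2 of 3 responders positive, the table is 2, 1 / 2, 16. Pearson chi-square = 21 × (2×16 − 1×2)² / (3×18×4×17) = 18,900/3,672 = 5.15, p = .023. The exact (Fisher) p is [C(4,2)×17 + C(4,3)]/C(21,3) = (102 + 4)/1,330 = .080.
- If one of those responders falls below 5%, the table is 1, 2 / 2, 16. Chi-square = 21 × (1×16 − 2×2)² / (3×18×3×18) = 3,024/2,916 = 1.04, p = .31.

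A rank test would change only by the number of patients whom that reading overtakes.

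**Large-sample information kept after a cut.** For a normal shift and a share q above the cut, efficiency relative to the t-test is φ(z)²/[q(1−q)]. At q = .20, z = .842 and φ = .280, which gives .0784/.16 = .49. Relative to Mann-Whitney, divide by 3/π, which gives .51. Against the t-test, the figure is .22 at q = .05, .34 at .10, .60 at .34 and .64 at .50. At 20% positive, about half is lost.

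**Power in samples of this size (simulation).** Assumptions: PD-L1 is normal on some latent scale, responders are shifted upward, and the cut is placed so that the stated share of all patients is positive.

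| Responders / n | Share positive | Shift | Exact Mann-Whitney | Pearson (planned) |
|---|---|---|---|---|
| 3/21 | 20% | 1.5 SD | .56 | .55 |
| 3/21 | 20% | 1.0 SD | .29 | .31 |
| 3/21 | 50% | 1.5 SD | .56 | .34 |
| 4/27 | 20% | 1.5 SD | .71 | .67 |
| 5/21 | 20% | 1.5 SD | .72 | .61 |

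Simulation error is about ±.01. The 20% figure is the only one that the analytical plan offers, and it is unclear whether it counts blasts or patients. The shifts are my assumptions.

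**The case against.** The strongest reply is that the plan loses little. At 3 of 21 responders and 20% positive, the planned Pearson test has almost the same power as Mann-Whitney at 1.5 SD and is marginally ahead at 1.0 SD. That is right. A reader might infer that the cut throws away most of the information; the figures do not support that. Larger gaps appear against Fisher's exact test (power about .39 in the first row of the table), but the plan does not use Fisher here, and much of that gap reflects Fisher's conservatism in sparse tables.

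A reader might also infer that the 2x2 table uses the baseline sample. The documents do not say so: PD-L1 is assayed at the start, after cycle 1, after every two combined cycles and at progression or discontinuation, and no time point is named for the table.

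Nor is it right that Aim 2 contains nothing beyond the table. The correlation of PD-L1 change with response and the mixed models may use the full scale. They concern change over time, however, and no test of PD-L1 level is specified there.

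Finally, the 5% cut is prespecified and referenced, the aim is exploratory, and no decision rule depends on it. All of this stands and limits the importance of the point. It does not explain why PD-L1 is left out of the comparison that Aim 1 gives its own markers.

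**Conclusion.** The point holds as a minor improvement. The only specified test of PD-L1 level against response rests on a 5% dichotomy of a measured quantity, and with about three responders its result can hinge on one borderline patient. Under the assumed normal shift, the power gained over the planned test runs from nothing (1.0 SD, 20% positive) through 1 to 11 points (1.5 SD, 20% positive, depending on the number of responders) to about 22 points (1.5 SD, 50% positive). The full-scale test has the practical merit that its power does not depend on the share of patients above 5%, which the documents do not clearly give. With so few responders, either test is weak.

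**What to change.** In the Appendix J analytical plan for Specific Aim 2:

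- Name the time point for the association test, for example the pre-treatment sample.
- Add an exact Mann-Whitney comparison of measured PD-L1 between responders and non-responders, with the AUC and its 95% confidence interval.
- Apply it to the IHC percentage or QIF score as well as to the flow percentage. The pitfalls paragraph for Aims 2 and 3 gives Aim 3 first call on scarce aspirate, so flow data for PD-L1 may be missing.
- Keep the 5% table as a secondary display for comparison with earlier studies.

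The cost is one or two sentences, with no new samples, assays or patients. The downsides are one more exploratory analysis and slightly less power if the true effect is a threshold at exactly 5%. Making the change before response data are examined avoids a post hoc choice of scale.

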9. BIOMARKER, CORRELATIVE, AND SPECIAL STUDIES

9.1 Exploratory/Ancillary Correlative Studies

Site(s) Performing Correlative Study.

The samples will be analyzed at the Yale Cancer Center

Collection and Handling of Specimens

All operating procedures for specimen collection, handling and storage will be standardized. Common standardized operating procedures (SOPs) will be to collect 15 cc of bone marrow (BM) (3 EDTA tubes) and 15 cc of blood (3 EDTA tubes) from the patient at baseline (before cycle 1), after cycles 1 (entinostat alone) and then every 2 cycles of entinostat and Pembrolizumab (MK-3475) dose. If a patient disease progresses, an additional 15 cc of blood and 15 cc of the BM will be obtained. For a patient that progresses and is removed from study treatment, additional blood or BM may be obtained at the time of routine collection. At the time of collection, tubes must be thoroughly mixed to prevent clotting. The specimen should be delivered to the Hematology Tissue Bank (PI: [name]) at Yale University within 24 hours after collection. Typically, fresh specimens (before cryopreservation) will be used for experiments. Specimens should be labeled with the patient's initials, study number, sample collection date and time, and sample source (peripheral blood or bone marrow). All data should be kept in laboratory log.

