HYPOTHESIS: We hypothesize that the HDACi ENT can reduce the quantity and suppressive function of MDSCs in BM of MDS patients who fail to get responses from DNMTi. We also hypothesize that ENT with have a synergistic effect with the anti-PD-1 antibody pembrolizumab leading to meaningful clinical responses when used in combination. The objective of this proposal is to assess the *in vivo* effects of the combined therapy with PD1 blockade and HDACi on three exploratory immunologic endpoints through correlative and mechanistic studies of samples collected from BM of treated patients.

SPECIFIC AIMS:

Aim 1. Assess the dynamic changes in MDSCs (quantitative and qualitative) in relation to ENT/anti-PD1 combined therapy and its correlation with the clinical response.

Aim 2. Evaluate PD-L1 expression in CD34+ blasts from human MDS BM and its correlation with the response to anti-PD1 therapy.

Aim 3. Characterize functional dynamics of immune cell subsets in MDS BM following ENT and anti-PD1 treatment.

Successful completion of these studies will describe the pembrolizumab-induced reprogramming in T-cell populations, assess whether these changes correlate with clinical events, provide critical insights into the future wider use of PD-1 blockade-based immunotherapy in patients with MDS and other myeloid malignancies, and demonstrate the significance of targeting MDSCs via HDACi.

PRELIMINARY DATA/PRIOR STUDIES:

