
Exploratory biomarkers to predict the response to anti-PD1 therapy in MDS: Compared to a murine model for linear T-cell differentiation, we have had to rely on cross-sectional assessment to define memory T-cell subsets. More than two markers (CD45RA, CCR7) enabled us to delineate memory T-cell compartments⁶⁹. For instance, we simply divide T-cells into four subsets: naïve

(CD45RA+CCR7+), central memory (CD45RA-CCR7+), effector memory (CD45RA-CCR7-), late effector (CD45RA+CCR7-)⁶⁹. The ratio of T_{CM} (CD45RA-CCR7+) to T_{EMRA} (CD45RA+CCR7-) and of T_{EM} (CD45RA-CCR7-) to T_{EMRA} (CD45RA+CCR7-) will be assessed in BM and peripheral blood using flow cytometry. More recent preclinical data suggest that the frequency of CD8+, and CD8+/regulatory T cells (Tregs) are two important predictive markers for anti-PD1 therapy⁷⁰. Additionally, this study also demonstrated exhausted CD8+ T cells defined by the expression of PD-1 and Eomes are reinvigorated, which can be defined by increased Ki67 and GzmB, following anti-PD1 and anti-CTLA4 treatment in a murine model. In **specific aim 3**, we will determine whether known biomarkers predict the response to anti-PD1 therapy in MDS.

METHODOLOGY OF CORRELATIVE STUDIES (EXPLORATORY BIOMARKERS): Specific Aim 1. Determine the numeric and functional alterations of MDSCs in relation to ENT/anti-PD1 therapy and their correlations with the clinical response

Human MDSCs are defined by a cross-sectional assessment of well-known surface markers with functional phenotype. Initially, the expression of a common myeloid marker, CD33 without the expression of the lymphoid cell markers (CD3, CD19, CD56) defined human MDSCs⁶³. Subsequent studies classified human MDSCs by HLA-DR-/Lineage-⁷¹, HLA-DR-/Lineage-/CD33+⁷²⁻⁷⁴, HLA-DR-/Lineage-/CD33+/CD11b+⁶⁵, CD14-/CD15+/CD33+/CD11b+⁷⁵, or HLA-DR-/CD14⁷⁶⁻⁸⁰. These heterogeneous definitions of human MDSCs cause a fundamental caveat especially in human correlative studies, suggesting that the most clinically relevant markers should be determined. Moreover, sample processing such as cryopreservation has been reported to affect some expression of surface markers and the suppressive function of human MDSCs⁸¹. Thus fresh BM aspirate will be assessed with flow cytometry to avoid any artifact from cryopreservation process.

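### Aim 3 asks about change before and after anti-PD1, but its only named contrast starts from a baseline taken before the entinostat run-in, so entinostat and pembrolizumab effects are mixed

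*Combined protocol and SAP*

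**What the plan says.** Appendix J words Aim 3 in more than one way. Under Specific Aims it is to "Characterize functional dynamics of immune cell subsets in MDS BM following ENT and anti-PD1 treatment". The methodology heading is narrower: "Characterize functional dynamics of immune cell subsets in MDS patients pre- and post- anti-PD1 therapy". The text closing the Specific Aims says the studies will "describe the pembrolizumab-induced reprogramming in T-cell populations, assess whether these changes correlate with clinical events". The background on exploratory biomarkers adds that in Aim 3 "we will determine whether known biomarkers predict the response to anti-PD1 therapy in MDS".

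Two analyses are stated:
- The statistical paragraph for Aim 3 lists eight measures (CD8+, CD4+, Foxp3 Tregs, the CD8+/Foxp3+ Treg measure, two memory-to-late-effector ratios, and Ki67 and GzmB in PD-1+ Eomes+ CD8 cells). The analysis is "to compare changes over time from baseline to several time-points will be performed by using mixed effects modelling", with a Benjamini-Hochberg correction. The false discovery level and the family are not given.
- The Aim 3 methodology ends with "The changes in these subsets will be correlated with clinical responses". No test, time point or multiplicity rule follows.

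Section 9.1 sets sampling "at baseline (before cycle 1), after cycles 1 (entinostat alone) and then every 2 cycles of entinostat" plus pembrolizumab. Baseline is therefore before entinostat, and a separate sample exists after entinostat alone and before the first pembrolizumab dose.

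**The concern.** Under the methodology wording, the pre-treatment state is the state just before pembrolizumab. The named contrast starts one full entinostat cycle earlier. If entinostat alone moves a T-cell marker, the baseline contrast shows that movement at every combination visit, and nothing in the paragraph separates it. A shift caused by the run-in could then be read as the work of the antibody.

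Sections 5.1 and 13.1 say the run-in exists to tell entinostat effects from combination effects. That is written for MDSCs, and the Aim 3 paragraph does not carry it over to T cells.

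The second, smaller gap is the response question. Aim 1 names a t-test or Mann-Whitney comparison of responders with non-responders, extended only to its own sub-aims 1.3 and 1.4. Aim 2 names a chi-square test. Section 13.4 covers MDSCs and adds nothing for Aim 3. The goal of predicting response thus has no method.

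**Working it through.** **The plan's own figure.** Aim 3 has no stated sample size or power. The nearest figure is the response rule in Section 13.2: 2 or more responses, 1% against 15%, 21 to 27 patients. The exact binomial P(X ≥ 2) is:
- n = 21: .0185 at 1% and .845 at 15%.
- n = 27: .0297 at 1% and .928 at 15%.

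These agree with the stated .02 to .03 and .84 to .93. No printed figure is disputed.

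**What the contrast estimates.** Let m0, m1 and mk be the marker means at baseline, end of cycle 1 and a combination visit. Then

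mk − m0 = (m1 − m0) + (mk − m1).

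The first term is the entinostat run-in change. The second is the change once pembrolizumab is added. The paragraph names the sum; the methodology wording asks for the second term.

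**Size, as an illustration.** These assumptions are not in the documents: 21 complete pairs, a two-sided paired t-test, mk − m1 = 0, and m1 − m0 equal to d standard deviations of the within-patient change, stable after cycle 1. The noncentrality is d√21 on 20 degrees of freedom.

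| d | noncentrality | P(significant), 5% (critical value 2.086) | P(significant), .05/8 = .00625 (critical value 3.055) |
|---|---|---|---|
| 0.5 | 2.291 | .59 | .26 |
| 0.8 | 3.666 | .94 | .72 |

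The last column is the first Benjamini-Hochberg step for eight measures at an assumed 5% false discovery level. With an assumed 15 pairs the ranges fall to .44 to .82 and .15 to .48.

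If d is instead in standard deviations of the marker itself, the change has standard deviation √(2(1 − r)), where r is the within-patient correlation. At r = .5 this equals 1 and the table stands. Over r = .3 to .7, the 5% figures are .45 to .80 for d = 0.5 and .84 to .99 for d = 0.8.

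A random-intercept mixed model with categorical visit was also simulated (300 runs, n = 21, r = .5, entinostat-only shift 0.8). The baseline contrast rejected in 95% of runs. The end-of-cycle-1 contrast rejected in 7%, close to nominal.

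**The response comparison.** At a 15% response rate, 21 × .15 = 3.15 responders are expected. P(2 or fewer of 21) = .0329 + .1221 + .2155 = .37. The smallest two-sided exact rank-test p-value under complete separation is 2/C(21, r) for r responders:
- r = 1: 2/21 = .095.
- r = 2: 2/210 = .0095, above .00625. A single marker cannot pass the first step. At least two markers would need to separate completely, since the second step is 2 × .05/8 = .0125.
- r = 3: 2/1330 = .0015, below .00625, but only if all three responders separate completely from the other 18.

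The family may exceed eight, because two time points and both marrow and blood could count.

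**The case against.** Much of the opposing case stands.

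First, a reader might infer that Aim 3 has no analysis against response and that change from baseline answers none of its questions. The documents do not support that. The methodology and the Specific Aims both commit to correlating changes with response, so the gap is an unnamed method. Change from baseline also directly answers Aim 3 as listed under Specific Aims, which covers both drugs together.

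Second, a reader might infer that the planned changes could never predict response. The change from baseline to end of cycle 1 is complete before pembrolizumab starts, so it could.

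Third, the paragraph speaks of several time points, and end of cycle 1 is a sampling visit. A mixed model with visit effects could produce the needed contrast. That is true, but the contrast is not specified, and the only reference named is baseline.

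Fourth, an end-of-cycle-1 reference does not isolate pembrolizumab. Entinostat continues alongside it and there is no control arm, so an entinostat effect still developing after cycle 1 would load on the later contrast. The nominal error rate above depends on that effect being stable.

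Finally, the aims are exploratory, and about three responders are expected. That limits the weight of the point but does not remove the mismatch between question and contrast.

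**Conclusion.** The point holds in this form: the one contrast named for Aim 3 does not match the methodology's question of change before and after anti-PD1, because it includes the entinostat run-in. Under the stated assumptions, with 21 pairs, a pure entinostat effect would be significant with probability .59 to .94 unadjusted, or .26 to .72 at .05/8. The shift sizes and the stability after cycle 1 are assumptions, so these figures show what could happen and are not forecasts. It does not follow that an entinostat effect will be misreported; the plan simply does not prevent it.

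The missing method for response is secondary. With a .37 chance of 2 or fewer responders among 21 at a 15% rate, any such comparison can only be exploratory.

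The MTD determination and the response-rate test are not affected.

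**What to change.** In the Aim 3 statistical paragraph of Appendix J:

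1. Treat visit as categorical. Use end of cycle 1 as the reference for visits after pembrolizumab starts, and report baseline to end of cycle 1 separately as the entinostat run-in change.
2. State that the first contrast estimates adding pembrolizumab to continued entinostat, without a control arm, and not pembrolizumab alone.
3. Name the response analysis: compare marker values at baseline and at end of cycle 1 between responders and non-responders by an exact rank test. Apply Benjamini-Hochberg with a stated level, over a family that counts markers, time points and tissues. Label it exploratory.
4. Reconcile the cycle 1 entinostat schedule. The notes under the Section 10 calendar give days 1, 8 and 15, while Section 13.1 gives days 1 and 8 for dose level 1. This affects what the end-of-cycle-1 sample represents.

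The cost of items 1 to 3 is wording and a few model contrasts; no new samples, visits or patients are needed. The downside is that patients without an end-of-cycle-1 sample contribute less to the main contrast. The change should be made before the marker data are analysed, so that it counts as prespecified.
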